## 4. STUDY DESIGN

### 4.1. Overall Design

The study will be a multi-centre, open-label single arm trial. Patients with severe eosinophilic asthma who are receiving omalizumab, but are not optimally controlled will be eligible to participate and will be identified through the ACQ-5 with a screening (Visit 1) and baseline (Visit 2) score of  $\geq 1.5$  and a history of  $\geq 2$  exacerbations in the past 12 months. For those subjects receiving omalizumab for  $\geq 8$  months, at least 1 exacerbation must be while on omalizumab treatment.

Subjects meeting all the inclusion/exclusion criteria at screening Visit 1, will enter a run-in period for a minimum of one week and up to 4 weeks to assess subjects' eligibility and compliance with study-related procedures.

[figure not shown]
Subjects will remain on their current maintenance therapy throughout the run-in period, including omalizumab. At Visit 2 subjects will discontinue omalizumab treatment and be switched to mepolizumab 100 mg SC every 4 weeks. Except for omalizumab, subjects will remain on their current maintenance therapy throughout the open-label treatment period.

Every subject, including those who withdraw early from the study, will be asked to return for an Exit Visit approximately 4 weeks after their last dose of study treatment.

An Exit interview will be conducted during the Exit Visit or early withdrawal Visit in a subset of participating sites and in a subset of patient who consent to participate.

The investigator is responsible for ensuring that consideration has been given to the post-study care of the patient's medical condition. At the end of the study, subjects may be prescribed appropriate alternative asthma therapy if needed and as determined by the study Investigator.

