
 Adjusted means and the corresponding 95% confidence intervals will be presented by visit The estimated adjusted means will be presented using the observed marginal distributions of the sample covariates (OM option in LSMEANS statement). The Kenward and Roger method for approximating the denominator degrees of freedom and correcting for bias in the estimated variance-covariance of the fixed effects will be used (DDMF=KR). An unstructured covariance structure for the R matrix will be used by specifying 'type=UN' on the REPEATED line. Change from the baseline at each Visit X will be calculated by (Estimated Score at Visit X minus Estimated Score at Baseline) and the corresponding 95% confidence intervals. Adjusted means at each visit will also be presented. Plots of Least Squares (LS) mean change from baseline pre- and post bronchodilator FEV1 and 95% confidence intervals from the model will be generated at each visit.
On-treatment Phase
• See Primary Efficacy Statistical Analysis, Section 7.1.2

Other Statistical Analyses
Other Endpoint
• Subject rated response to therapy at Week 32
• Clinician rated response to therapy at Week 32
Results Presentation

 • The number and percentage of subjects in each response category will be presented for each visit. • The number of subjects with a missing responses at each visit will be presented in a separate category.
--

On-treatment Phase

 • An On-Treatment “de jure” analysis will also be performed which does not consider any data collected following treatment discontinuation (see On-Treatment definition within Section 10.4).

Other Statistical Analyses

Other Endpoint

 • Mean change from baseline in Treatment Satisfaction Questionnaire for Medication (TSQM-9)

Model Specification

 • The Mean Change at Week 32 will be tested to see if it is significantly different from zero using Wilcoxon signed-rank test

Model Checking & Diagnostics

 • Check for the extreme outliers by plotting the differences between TSQM-9 at Week 32 and Baseline

Model Results Presentation

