eCRF/ paper diary/worksheet												
Complete eCRF	x	x	x	x	x	x	x	x	x	x	x	
Dispense paper diary/worksheet	x	x	x	x	x	x	x	x	x	x		
Collect/review paper diary/worksheet		x	x	x	x	x	x	x	x	x	x	
1. Pre-screen Visit 0 must be completed prior to Visit 1 (Screening). It can be completed on the same day as Visit 1 or at up to 2 weeks prior to Visit 1. 2. Subjects will be assigned a subject number at the time ICF signed. The ICF must be signed before any study procedures including medication wash out period(s). 3. Exit Visit may be completed 3 to 5 weeks post last dose. 4. Therapy history to include a detailed review of prior biologics received for treatment of asthma, including omalizumab dose and regimen and prior investigational therapies e.g anti-IL5 or anti-IL13 preparations. 5. All study efficacy, safety and all patient reported questionnaires must be completed prior any study procedure. 6. Spirometry to include pre- and post bronchodilator FEV1 from V2. 7. Exit interview will be conducted only in a subset of sites and in a subset of subjects who choose to participate in the Exit interview. Subjects must be consented prior to interview 8. Parasitic screening is only required in countries with high-risk or for subjects who have visited high-risk countries in the past 6 months. Sites should use local laboratories. 9. Pharmacogenetic sample may be drawn at Visit 2 or any at any visit after. 10. Pregnancy test, U= urine 11. Hepatitis B Surface Antigen and Hepatitis C antibody. (if hepatitis C antibody is positive, hepatitis C will be confirmed by PCR)												

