10.4.2. Treatment Phases (Visit Based Efficacy Data)

Efficacy data collected at scheduled visits (including: Questionnaires, PFT, Blood Eosinophils and Biomarkers) will be classified according to time of occurrence/assessment relative to the first and last date of mepolizumab and the attendance dates of specific visits.

Treatment Phase	Definition
Pre-Treatment	Visit date/time ≤ First dose of mepolizumab
On-Treatment	Subjects completing treatment and completing the study: Visit date/time < First dose of mepolizumab ≤ Visit 10 (Exit Visit)* visit date/time Subjects discontinuing study treatment/withdrawing early from the study: Visit date/time < First dose of mepolizumab ≤ Earliest of (1) Last dose of mepolizumab + 28 days or (2) Early Withdrawal/Treatment Discontinuation visit date date/time
Off-Treatment	Subjects completing treatment and completing the study: Date & time > Visit 10 (Exit Visit)* visit date/time Subjects discontinuing study treatment/withdrawing early from the study: Date & time > Earliest of : (1) Last dose of mepolizumab + 28 days or (2) Early Withdrawal/Treatment Discontinuation visit date/time

* Data may be considered off treatment if beyond acceptable protocol defined limits.

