2.29.	ITT	SHELL	Analysis of Change from Baseline in Blood Eosinophils (10 ⁹ /L) (on-treatment data only)		SAC
Pre – Bronchodilator and Post – Bronchodilator FEV1					
2.30.	ITT	SHELL	Summary of Clinic Pre-Bronchodilator FEV1 (mL)	See Efficacy Table 2.27 (MID200862 'final' reporting effort), but exclude 'Placebo' column	SAC
2.31.	ITT	SHELL	Analysis of Change From Baseline in Clinic Pre-Bronchodilator FEV1 (mL)	See Efficacy Table 2.28 (MID200862 'final' reporting effort), but exclude 'Placebo' column and Difference Analysis	SAC
2.32.	ITT	SHELL	Summary of Clinic Post-Bronchodilator FEV1 (mL)	See Efficacy Table 2.49 (MID200862 'final' reporting effort), but exclude 'Placebo' column	SAC
2.33.	ITT	SHELL	Analysis of Change From Baseline in Clinic Post-Bronchodilator FEV1 (mL)	See Efficacy Table 2.68 (MID200862 'final' reporting effort), but exclude 'Placebo' column and Difference Analysis	SAC
Response to Therapy					
2.34.	ITT	SHELL	Summary of Subject Rated Overall Evaluation of Response to Therapy (on-treatment data only)	See Efficacy Table 2.47 (MID200862 'final' reporting effort), but exclude 'Placebo' column and Odds Ratio Analysis	SAC

Efficacy: Tables					
No.	Population	IDSL / TST ID / Example Shell	Title	Programming Notes	Deliverable [Priority]
2.35.	ITT	SHELL	Summary of Clinician Rated Overall Evaluation of Response to Therapy (on-treatment data only)		SAC
Treatment Satisfaction Questionnaire for Medication (TSQM-9)					
2.36.	ITT	SHELL	Summary of Treatment Satisfaction Questionnaire for Medication (TSQM - 9) (on-treatment data only)	Summarise the Effectiveness, Convenience and Overall Satisfaction scales separately	SAC
Biomarkers					
2.37.	ITT	SHELL	Summary of CCL13 (on-treatment data only)		SAC
2.38.	ITT	SHELL	Summary of CCL17 (on-treatment data only)		SAC
2.39.	ITT	SHELL	Summary of ECP (on-treatment data only)		SAC
2.40.	ITT	SHELL	Summary of EDN (on-treatment data only)		SAC
2.41.	ITT	SHELL	Summary of Eotaxin1 (on-treatment data only)		SAC
2.42.	ITT	SHELL	Summary of Total IL-5 (on-treatment data only)		SAC
2.43.	ITT	SHELL	Summary of IL-13 (on-treatment data only)		SAC
2.44.	ITT	SHELL	Summary of MDC (on-treatment data only)		SAC
2.45.	ITT	SHELL	Summary of Periostin (on-treatment data only)		SAC
2.46.	ITT	SHELL	Summary of TSLP (on-treatment data only)		SAC

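### The SAP ends the on-treatment window earlier for discontinuers than for completers, and response ratings, TSQM-9 and biomarkers have no all-data display to catch what is cut

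*SAP*

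**What the plan says.** **Phase definitions (SAP 10.4.2).** For subjects who complete, the on-treatment row reads "Visit date/time < First dose of mepolizumab ≤ Visit 10 (Exit Visit)* visit date/time". The inequality is written in the wrong order, but the end point is plain: the Exit Visit. The footnote adds: "Data may be considered off treatment if beyond acceptable protocol defined limits". For subjects who discontinue or withdraw, the phase ends at the earlier of (1) "Last dose of mepolizumab + 28 days or (2) Early Withdrawal/Treatment Discontinuation visit date date/time". The off-treatment row states the same limit without ambiguity: "Date & time > Earliest of : (1) Last dose of mepolizumab + 28 days or (2) Early Withdrawal/Treatment Discontinuation visit date/time".

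**Visit timing.** Footnote 3 of the Time and Events table is attached to the combined Exit/Early Withdrawal column, in both the protocol (7.1) and the SAP (10.2.1): "Exit Visit may be completed 3 to 5 weeks post last dose". Protocol 4.1 sets one target for all: "Every subject, including those who withdraw early from the study, will be asked to return for an Exit Visit approximately 4 weeks after" the last dose.

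**Displays.** SAP Table 5 gives the response ratings, TSQM-9 and biomarkers an on-treatment row and no other. The titles of Tables 2.34 to 2.46 carry the same restriction, for example "Summary of Subject Rated Overall Evaluation of Response to Therapy (on-treatment data only)". Yet SAP 8.1.2 says of each of these endpoints that an on-treatment "analysis will also be performed which does not consider any data collected following treatment discontinuation". The word *also* implies a main analysis that is not listed. SAP 10.7.1 says that, unless specified otherwise, a withdrawn subject's available data up to withdrawal go into the summary tables, and that all such data are listed.

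**The concern.** Two subjects seen on the same permitted day after their last dose are treated differently. The completer's assessment counts as on-treatment and the discontinuer's does not. For most efficacy endpoints this only moves a value between two analyses, because an all-data analysis also exists. For the response ratings, TSQM-9 and biomarkers, the on-treatment display is the only one, so the value disappears from the report.

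The gap is wider than days 29 to 35. Protocol 5.5.1 asks subjects who stop mepolizumab to attend their remaining visits where safe. What they report at those visits is properly off-treatment, but for these endpoints it too is shown nowhere.

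The study is open-label with a single arm, so no comparator loses data in the same way, and lack of efficacy is a listed reason for stopping. The Week 32 change in TSQM-9 is also tested, by a signed-rank test with a p-value (SAP 8.1.2), so for that endpoint more than a descriptive table is involved.

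**Working it through.** **1. Inputs.** Visit window: 4 weeks ± 7 days, also given as 3 to 5 weeks (Protocol 7.1, SAP 10.2.1). Phase limits: SAP 10.4.2. Treated subjects 120 and withdrawal rate 15% (Protocol 4.3).

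**2. The plan's own figures.** 28 − 7 = 21 and 28 + 7 = 35, which equal 3 × 7 and 5 × 7, so the two statements of the window agree. Planned withdrawals: 0.15 × 120 = 18. Completers: 120 − 18 = 102, against the stated figure of about 100.

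**3. The rule applied to each permitted day.** A discontinuer's visit is off-treatment if its day exceeds min(28, visit day).

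| Days after last dose | Completer's Exit Visit | min(28, visit day) | Discontinuer's withdrawal visit |
|---|---|---|---|
| 21 to 28 | on-treatment | visit day | on-treatment |
| 29 to 35 | on-treatment | 28 | off-treatment |

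Permitted days: 35 − 21 + 1 = 15. Affected days: 35 − 29 + 1 = 7. Share: 7/15 = 46.7%. Because 10.4.2 works in date and time, a visit late on day 28 could also fall outside if the last dose was given earlier in the day.

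**4. How many subjects.** If all 18 attend and their visits are spread evenly over the 15 days, 18 × 7/15 = 8.4, or about 8. The documents give no distribution of visit days. The range is 0 (none attends after day 28) to 18 (all attend on days 29 to 35). Subjects who stop mepolizumab but stay in the study come on top, and the documents give no planned number for them.

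**5. What an affected subject still contributes.**

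| Endpoint | Post-baseline assessments | Planned display | What remains |
|---|---|---|---|
| Response ratings | three earlier visits, Exit/Early Withdrawal | on-treatment only | earlier ratings, if reached |
| TSQM-9 | Exit/Early Withdrawal only | on-treatment only | nothing |
| Biomarkers | Visit 4, Exit/Early Withdrawal | on-treatment only | Visit 4, if reached |
| ACQ-5, SGRQ, FEV1 | several | on- and off-treatment | not cut by the phase rule |
| Eosinophils, exacerbations | several or continuous | both versions | not cut in the all-data version |

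Listings do not fill the gap. The only efficacy listings planned are ACQ-5 and exacerbations (Listings 9 and 10).

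**6. After the change.** With the limit at day 35 for both groups, min(35, visit day) equals the visit day throughout, so 0 of 15 permitted days are off-treatment.

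**The case against.** **Twenty-eight days is a reasonable limit.** It is the dosing interval and the adverse-event limit in SAP 10.4.3. For exacerbations it follows protocol 7.3.2.4, which stops collection for early leavers at about 4 weeks after the last dose. This stands for 10.4.1, which should not be changed. It does not explain 10.4.2: the adverse-event rule applies one limit to everyone, whereas 10.4.2 applies two.

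**A reader might infer that response and satisfaction are overstated.** The documents do not support that. SAP 8.1.2 reports missing ratings as a separate category, and SAP 10.5.3 lists both N and n without saying which is the percentage base. If the base is all ITT subjects, moving an answer to missing cannot raise the percentage improved. If the base is non-missing answers, the percentage rises only if those removed did worse than the rest. That is plausible for subjects who stop, but the documents give no data on it.

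**Slotting may exclude the same values anyway.** Under SAP 10.3.2, early-withdrawal data go to the scheduled visit or the nearest one at which the endpoint was due, if that visit is empty. An early leaver would often not reach the Week 32 row whatever the cut-off. For TSQM-9 the nearest slot may be Visit 1, normally already filled. This stands: the 28-day limit is not always the only cause.

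**The number may be small.** Some withdrawals are losses to follow-up with no visit, and visits target day 28. This stands too, and is why only a range can be given.

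**The endpoints are minor.** They are classed as other or exploratory. That is true and limits the consequence. It does not justify collecting data that no display will show.

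**Conclusion.** The point holds as a gap in display and an inconsistency in definition. A discontinuer's visit on days 29 to 35 is on time under the protocol and off-treatment under SAP 10.4.2, while a completer's visit on the same day is on-treatment. For the response ratings, TSQM-9 and biomarkers, such values, and any from later visits after stopping mepolizumab, have no planned display. This sits badly with the wording of 8.1.2 and the general rule in 10.7.1.

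Withdrawal visits on days 21 to 28 are kept, apart from the time-of-day edge on day 28, so it would be wrong to read this as the loss of every discontinuer. The number lost is unknown within 0 to 18 planned withdrawals; about 8 rests on full attendance and an even spread. The direction of any bias is open.

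The primary ACQ-5 analysis, SGRQ and FEV1 use on- and off-treatment data and are unaffected. Exacerbations and eosinophils keep an all-data analysis. TSQM-9 is the most exposed. This is an inexpensive improvement worth making before database freeze, not a threat to the main conclusion.

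**What to change.** 1. Add on- and off-treatment ITT displays for Tables 2.34 to 2.36 and for biomarker Tables 2.37 to 2.46, with matching rows in Table 5, as already planned for ACQ-5, SGRQ and FEV1. Keep the on-treatment tables as supportive. This recovers most of what is lost and brings the display list into line with 8.1.2 and 10.7.1.
2. In 10.4.2 only, count a discontinuer's Early Withdrawal/Treatment Discontinuation visit as on-treatment if it falls within the protocol visit window (to day 35), as for completers. Put the on-treatment inequality in the right order in the same edit.
3. Leave 10.4.1 unchanged, so that it stays consistent with protocol 7.3.2.4.

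The cost is SAP wording and 3 + 10 = 13 repeated tables on existing shells, with no new data collection. The downside is that up to 7 more days after the last dose count as on-treatment for discontinuers, as they already do for completers. This also carries into the on-treatment eosinophil analysis (Table 2.29). Neither change alters slotting under 10.3.2, which may still keep some early leavers' values out of the Week 32 row.

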10.4.3. Treatment Phases (Adverse Events)

Adverse events will be classified according to time of occurrence relative to the first and last date of the study treatment.

Treatment Phase	Definition
Pre-Treatment	AE Onset Date & time < First dose of mepolizumab If mepolizumab treatment is never started then all AEs will be classified as pre-treatment.
On- Treatment	First dose of mepolizumab ≤ AE Onset Date & time ≤ Last dose of mepolizumab + 28 days If an AE start date is missing or partial then the AE will be considered on-treatment unless there is evidence to the contrary (e.g. month/year of onset date is present and is earlier than the month/year of First dose of mepolizumab).
Post-treatment	AE Onset Date & time > Last dose of mepolizumab + 28 days

10.4.3.1. Adverse Event Data Derivations

Treatment State	Definition
Onset Time Since 1 st Dose (Days)	If Treatment Start Date > AE Onset Date = AE Onset Date - First dose of mepolizumab If Treatment Start Date ≤ AE Onset Date = AE Onset Date - First dose of mepolizumab +1 If Treatment Start Date or AE Onset Date is missing = missing.
Duration (Days)	AE Resolution Date – AE Onset Date + 1
Drug-related	If relationship is marked 'YES' on Inform/eCRF OR value is missing.

10.4.4. Treatment Phases (Concomitant Medications)

Concomitant medications will be classified according to time of occurrence relative to the first and last date of the study treatment.

Treatment/Study Phase	Definition
Taken Before the Run-in	If Con-med Start Date < Date of Visit 1
Taken During the Run-in	
 • If Con-med Start Date < Date of Visit 1 and Con-med Stop Date ≤ Date of Visit 1, or • If Date of Visit 1 ≤ Con-med Start Date < First dose of mepolizumab
Taken During Treatment	
 • If Con-med Start Date < First dose of mepolizumab and Con-med Stop Date ≥ First dose of mepolizumab or • If First dose of mepolizumab ≤ Con-med Start Date ≤ Last dose of mepolizumab + 28 days • If the con-med start or stop date is missing or partial then the con-med will be considered on-treatment unless there is evidence to the contrary (e.g. month/year of con-med stop date is present and is before the month/year of the first dose of mepolizumab).
Started During Treatment	Subset of con-meds Taken During Treatment for which: First dose of mepolizumab ≤ Con-med Start Date ≤ Last dose of mepolizumab + 28 days
Taken Post Treatment	
 • Last dose of mepolizumab + 28 days < Con-med Stop Date

A medication will be summarised in every treatment/study phase in which it was taken,

so for example a medication that was started in the run-in and stopped during treatment will appear in both the during the run-in and during treatment tables.

10.5. Appendix 5: Data Display Standards & Handling Conventions

10.5.1. Study Treatment & Subgroup Display Descriptors

Treatment Group Descriptions			
RandAll NG		Data Displays for Reporting	
Code	Description	Description	Order [1]
1	Mepolizumab 100mg SC	Mepolizumab 100mg SC	1

NOTES:

1. Order represents treatments being presented in TFL, as appropriate.

10.5.2. Baseline Definition & Derivations

10.5.2.1. Baseline Definition

- Baseline will be defined for all subjects who are within the ITT population.
- For all endpoints the baseline values for each assessment will be the latest available assessment prior to first dose of mepolizumab.
- Measurements on the same date as the first administration of mepolizumab will be considered within the baseline derivation if measurement time is not captured. Where the measurement time is captured this should be compared against the time of first receiving mepolizumab.

10.5.2.2. Derivations and Handling of Missing Baseline Data

Definition	Reporting Details
Change from Baseline	= Visit Value – Baseline
Ratio to Baseline	= Visit Value / Baseline

NOTES :

- Unless otherwise specified, the baseline definitions specified in Section 10.5.2.1 Baseline Definitions will be used for endpoints / parameters and indicated on summaries and listings.
- Unless otherwise stated, if baseline data is missing no derivation will be performed and will be set to missing.

10.5.3. Reporting Process & Standards

Reporting Process	
Software	

 • The currently supported versions of SAS software will be used. 	
Reporting Area	
HARP Server	: uk1salx00175
HARP Area	: /arenv/arprod/sb240563/mid204471/final01
Quality Control (QC) Spread sheet	: /arenv/arprod/sb240563/mid204471/final01/documents

Reporting Process	
Analysis Datasets	

 Analysis datasets will be created according to CDISC standards. For creation of ADaM datasets (ADCM/ADAE), the same version of dictionary datasets will be implemented for conversion from SI to SDTM. 	
Generation of RTF Files	

 RTF files will be generated only for summary tables. 	
Reporting Standards	
General	

 The current GSK Integrated Data Standards Library (IDSL) will be applied for reporting, unless otherwise stated: 
 4.03 to 4.23: General Principles 5.01 to 5.08: Principles Related to Data Listings 6.01 to 6.11: Principles Related to Summary Tables 7.01 to 7.13: Principles Related to Graphics 	
Formats	

 All data will be reported according to the actual treatment the subject received unless otherwise stated. The reported precision (decimal places) will follow the IDSL statistical principles but may be adjusted to a clinically interpretable number of decimal places. 	
Planned and Actual Time	

 Reporting for tables, figures and formal statistical analyses : 
 Nominal visits (planned time relative to dosing) will be used in figures, summaries, statistical analyses and calculation of any derived parameters, unless otherwise stated. The impact of any major deviation from the planned assessment times and/or scheduled visit days on the analyses and interpretation of the results will be assessed as appropriate. Reporting for Data Listings: 
 Planned and actual time relative to study drug dosing will be shown in listings (Refer to IDSL Statistical Principle 5.05.1). Unscheduled or unplanned readings will be presented within the subject's listings. Scheduled visits outside the protocol defined time-windows (i.e. recorded as protocol deviations) will be included in listings, summaries and statistical analyses. 	
Unscheduled Visits	

 When possible unscheduled assessments will be slotted to the closest adjacent scheduled visit. If an unscheduled visit occurs between two completed scheduled visits, the data from the unscheduled visit will not be used in summary tables which are based on by-visit assessments. The information from the unscheduled visit will be included in 'any time post-baseline' summaries and will also be presented in any relevant listings. See Section 10.3 for further details. 	
Descriptive Summary Statistics	
Continuous Data	Refer to IDSL Statistical Principle 6.06.1
Categorical Data	N (number of subjects in the treatment group), n (number of subjects with

Reporting Standards	
	non-missing values), frequency, %
Graphical Displays	
•	Refer to IDSL Statistical Principals 7.01 to 7.13.

